### **16.1.2. Unsolicited Adverse Events**

All unsolicited adverse events summaries will be reported by MedDRA, SOC and PT and will include non-serious unsolicited events, SAE and AESI. These summaries will exclude solicited AE starting within day 1 to 7 and continuing beyond day 7.

The verbatim reports of unsolicited AEs will be reviewed by a physician and the signs and symptoms will be coded according to the MedDRA Dictionary for Adverse Reaction Terminology version 25.1 or higher. Every verbatim term will be matched with the appropriate Preferred Term.

Unsolicited events will be summarized and listed as:

The number and percentage of participants, with exact 95% CIs, with any unsolicited AEs during the 21-day follow-up period (i.e., the day of vaccination and 20 subsequent days) will be tabulated following each vaccination and overall.

This summary will be repeated for:

- grade  $\geq$  3 unsolicited AEs,
- causally related unsolicited AEs
- causally related and grade  $\geq$  3 unsolicited AEs,

---

Document: \\ieedc-vnasc01\BIOSdata\GSK\H5N8(Flu)\HAB99808\Biostatistics\Documentation\SAP\SAP\SAP v5.0\GSK H5N8-219833\_SAP\_v5.0\_19AUG2024.docx

Author: PPD Version Number: 5.0

Version Date: 19AUG2024

Template No.: CS\_TP\_BS016 Revision 7

Reference: CS\_WI\_BS005

Effective Date: 01Nov2021

- unsolicited AEs resulting in a medically attended visit

A list of unsolicited AEs leading to study discontinuation or vaccine discontinuation will be tabulated by study intervention group by MedDRA, SOC and PT.

All unsolicited AEs will be included in a listing.

### **16.1.3.     Solicited and Unsolicited Adverse Events**

For clinicaltrials.gov and EudraCT posting purposes, the following summary will be produced:

The number and percentage of participants reporting any unsolicited adverse events with MedDRA PTs that are synonymous with solicited events, and starting after the end of each solicited period, will be summarized following each vaccination and overall and by severity (mild, moderate or severe). If a participant experiences an event on more than one occasion, the maximum intensity will be reported. **Error! Reference source not found.** shows the corresponding MedDRA LLTs that will be selected from the unsolicited adverse events for this analysis.

Table H:     Solicited events lower level term codes and decodes

Solicited event	Lower level term code	Corresponding Lower level term decode
Pain	10022086	Injection site pain
Erythema	10022061	Injection site erythema
Swelling	10053425	Injection site swelling
Fever	10016558	Fever
Headache	10019211	Headache
Fatigue	10016256	Fatigue
Myalgia	10028411	Myalgia
Arthralgia	10003239	Arthralgia
Chills	10008531	Chills
Nausea	10028813	Nausea
Vomiting	10047700	Vomiting
Diarrhoea	10012735	Diarrhoea
Abdominal pain	10000081	Abdominal pain

The number and percentage of participants, with exact 95% CIs, of combined solicited and unsolicited non-serious adverse events (all grades, Grade 3, medically attended) during the 21-day follow-up period (i.e., the day of

Document: \\ieedc-vnasc01\BIOSdata\GSK\H5N8(Flu)\HAB99808\Biostatistics\Documentation\SAP\SAP\SAP\SAP v5.0\GSK H5N8-219833\_SAP\_v5.0\_19AUG2024.docx

Author: PPD

Version Number: 5.0

Version Date: 19AUG2024

Template No.: CS\_TP\_BS016 Revision 7

Reference: CS\_WI\_BS005

Effective Date: 01Nov2021

vaccination and 20 subsequent days) will be produced by SOC and PT, according to occurrence of each event, following each vaccination and overall. The number of events will also be provided in which 2 events are considered different if they have different start date or PT name.

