10.8 Appendix 8: List of Potential Immune-Mediated Diseases

The GSK list of pIMDs is based on MedDRA version 26.1.

Table 16 GSK List of pIMD MedDRA Terms

MedDRA Term Name	Term Level
Acute cutaneous lupus erythematosus	PT
Acute disseminated encephalomyelitis	PT
Acute febrile neutrophilic dermatosis	PT
Acute flaccid myelitis	PT
Acute haemorrhagic leukoencephalitis	PT
Acute haemorrhagic oedema of infancy	PT
Acute macular neuroretinopathy	PT
Acute motor axonal neuropathy	PT
Acute motor-sensory axonal neuropathy	PT
Acute necrotising myelitis	PT
Addison's disease	PT
Administration site vasculitis	PT
AGEP-DRESS overlap	PT
Alopecia areata	PT
Alveolar proteinosis	PT
Ankylosing spondylitis	PT
Antibody-dependent enhancement	PT
Anti-glomerular basement membrane disease	PT
Anti-LRP2 nephropathy	PT
Anti-myelin-associated glycoprotein associated polyneuropathy	PT
Anti-neutrophil cytoplasmic antibody positive vasculitis	PT
Antiphospholipid syndrome	PT
Anti-RNA polymerase III antibody increased	PT
Anti-RNA polymerase III antibody positive	PT
Antisynthetase syndrome	PT
Aortitis	PT
Application site vasculitis	PT
Arteritis	PT
Arteritis coronary	PT

MedDRA Term Name	Term Level
Arthritis enteropathic	PT
Arthritis reactive	PT
ASIA syndrome	PT
Atrophic thyroiditis	PT
Autoimmune anaemia	PT
Autoimmune aplastic anaemia	PT
Autoimmune arthritis	PT
Autoimmune blistering disease	PT
Autoimmune cerebellar ataxia	PT
Autoimmune cholangitis	PT
Autoimmune colitis	PT
Autoimmune demyelinating disease	PT
Autoimmune dermatitis	PT
Autoimmune disorder	PT
Autoimmune encephalopathy	PT
Autoimmune endocrine disorder	PT
Autoimmune enteropathy	PT
Autoimmune eye disorder	PT
Autoimmune haemolytic anaemia	PT
Autoimmune heparin-induced thrombocytopenia	PT
Autoimmune hepatitis	PT
Autoimmune hyperlipidaemia	PT
Autoimmune hypothyroidism	PT
Autoimmune inner ear disease	PT
Autoimmune lung disease	PT
Autoimmune lymphoproliferative syndrome	PT
Autoimmune myocarditis	PT
Autoimmune myositis	PT
Autoimmune nephritis	PT
Autoimmune neuropathy	PT
Autoimmune neutropenia	PT
Autoimmune pancreatitis	PT
Autoimmune pancytopenia	PT

MedDRA Term Name	Term Level
Autoimmune pericarditis	PT
Autoimmune retinopathy	PT
Autoimmune thyroid disorder	PT
Autoimmune thyroiditis	PT
Autoimmune uveitis	PT
Autoinflammatory disease	PT
Axial spondyloarthritis	PT
Axonal and demyelinating polyneuropathy	PT
Axonal neuropathy	PT
Behcet's syndrome	PT
Bell's palsy	PT
Bickerstaff's encephalitis	PT
Birdshot chorioretinopathy	PT
Brachial plexopathy	PT

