Toxic epidermal necrolysis	PT
Trigeminal nerve paresis	PT
Trigeminal palsy	PT
Tubulointerstitial nephritis and uveitis syndrome	PT
Tumefactive multiple sclerosis	PT
Type 1 diabetes mellitus	PT
Uhthoff's phenomenon	PT
Ulcerative keratitis	PT
Undifferentiated connective tissue disease	PT
Undifferentiated spondyloarthritis	PT
Urticarial vasculitis	PT
Uveitis	PT
Vaccination site vasculitis	PT

MedDRA Term Name	Term Level
Vagus nerve paralysis	PT
Vascular purpura	PT
Vasculitic rash	PT
Vasculitic ulcer	PT
Vasculitis	PT
Vasculitis gastrointestinal	PT
Vasculitis necrotising	PT
VIth nerve paralysis	PT
VIth nerve paresis	PT
Vitiligo	PT
Vocal cord paralysis	PT
Vocal cord paresis	PT
Vogt-Koyanagi-Harada disease	PT
Warm autoimmune haemolytic anaemia	PT
XIth nerve paralysis	PT

Abbreviations: LLT=lowest level term; PT=preferred term.

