### Primary Safety Endpoints

#### Solicited events

- o Percentage of participants reporting each solicited administration site event (pain, erythema / redness, swelling) with onset within 7-days (i.e., day of vaccination and 6 subsequent days) following each vaccination and overall.
- o Percentage of participants reporting each solicited systemic event (fatigue, fever, headache, muscle ache, joint pain, shivering [chills], sweating, nausea, vomiting, diarrhea, abdominal pain) with onset within 7-days (i.e., day of vaccination and 6 subsequent days) following each vaccination and overall.

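### SAP 16.1.3 defines the late-onset registry summary by preferred term but selects events by one lower level term each, and Table H has no row for sweating

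*SAP*

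**What the plan says.** SAP 16.1.3 opens with a summary made for public registry posting. It counts participants "reporting any unsolicited adverse events with MedDRA PTs that are synonymous with solicited events, and starting after the end of each solicited period", after each vaccination and overall, by severity.

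The next step fixes how the events are found. A table, reached through a cross-reference that prints as an error message, "shows the corresponding MedDRA LLTs that will be selected from the unsolicited adverse events for this analysis". The only table in that section is Table H, titled "Solicited events lower level term codes and decodes". It has one code and one decode per event. The three local reactions appear with injection-site terms only, for example "Injection site erythema".

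Neighbouring text works at PT level. SAP 16.1.2 says of unsolicited events: "Every verbatim term will be matched with the appropriate Preferred Term". The second output of 16.1.3, the combined solicited and unsolicited non-serious events over 21 days, is also laid out by system organ class and PT.

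**The concern.** The definition and the selection rule sit in one paragraph at two levels of the MedDRA hierarchy. A programmer can follow the sentence (all synonymous PTs) or the table (13 listed LLTs), and the two can give different counts. The table is the narrower of the two, so following it can only remove events.

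The protocol (section 10.5.1 and the glossary) makes a solicited-type symptom with onset outside the solicited period an unsolicited AE. This summary is the one output meant to pick those events out for the public record. If the selection list is incomplete, the posted figure understates late-onset reactions of the solicited types. Nothing in the posted table would show that this had happened.

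**Working it through.** The plan attaches no figure to this output, so there is nothing to reproduce. The check is a comparison of texts and a count of rows.

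**1. Level of the definition against level of the selection (SAP 16.1.3).**
- Definition: PTs synonymous with solicited events.
- Selection: the LLTs in Table H.
- Extension rule: none. Nothing says that other LLTs under the same PT are also taken.

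An event whose PT is synonymous, but whose LLT is not one of the 13 listed, therefore meets the definition and fails the selection.

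**2. Completeness of Table H against Table E.**
- Table E: 3 local + 11 systemic = 14 solicited events.
- Table H: 13 rows.
- Matching by meaning (muscle ache to myalgia, joint pain to arthralgia, shivering to chills, diarrhea to diarrhoea) leaves 14 − 13 = 1 event without a row: sweating.

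Table H follows the order of Table E. In Table E sweating stands between shivering and nausea, while Table H goes straight from chills to nausea. The row is thus missing from inside the list and has not been cut off at its end. Late-onset sweating is never selected, whether Table H is applied at LLT level or through the PT of each listed term.

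**3. Site prefix for local reactions.**
- Table H: injection site, in all 3 local rows.
- SAP section 16, primary safety endpoints, uses another name: "Percentage of participants reporting each solicited administration site event (pain, erythema / redness, swelling".
- Protocol Appendix 8, Table 16 lists "Administration site vasculitis" and "Vaccination site vasculitis" as separate PTs, next to an injection-site counterpart.

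This shows that MedDRA separates site-specific PTs for vasculitis. It does not show that such PTs exist for pain, erythema or swelling, or that coders in this trial would use them.

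**4. Wording of the events.** The protocol's diary terms are redness, muscle ache, joint pain and shivering. Table H lists erythema, myalgia, arthralgia and chills. A late event reported in the diary's words could be coded to an LLT closer to those words. The documents do not say how it would be coded.

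**5. Size.** If n synonymous late-onset events occur and a share s is coded outside Table H, the number captured is n(1 − s) on average. With independent coding, the chance of missing at least one is 1 − (1 − s)^n. The documents give neither n nor s. With n = 5 assumed:

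| s (assumed) | captured on average | chance of missing at least one |
|---|---|---|
| 0 | 5 × 1.0 = 5.0 | 0% |
| 0.1 | 5 × 0.9 = 4.5 | 1 − 0.9^5 = 41% |
| 0.5 | 5 × 0.5 = 2.5 | 1 − 0.5^5 = 97% |

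The table only shows how the result moves with s. It is no estimate for this trial.

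**6. Where an unselected event still appears.** SAP 16.1.2 tabulates unsolicited AEs over 21 days by system organ class and PT and lists all of them. SAP 16.1.3 tabulates combined non-serious events over 21 days by system organ class and PT. None of these outputs is restricted to Table H.

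**The case against.** The best defence is that the PT sentence governs. On that reading Table H, whose title describes solicited events, is a code lookup for diary items, and the sentence about selection is loose drafting. The injection-site prefix also fits an intramuscular vaccine and the labels in Table E, which place all three local events at the injection site. Coding goes through a central dictionary with physician review of verbatim terms, so it may be uniform enough that no event falls outside the list. The sponsor may also choose a narrow list of synonyms.

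Much of this stands. The documents name no further LLT under the relevant PTs and show nothing of the coding conventions, so the loss through LLT or prefix is conditional.

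Two things do not yield. The text says that the listed LLTs are what will be selected, so the lookup reading goes against its plain words. And sweating is absent from the list under any reading that uses Table H at all.

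A reader might go further and infer that the registry count will be too low by some stated percentage, say 10% to 50%. The documents do not support that: such a range only restates an assumed s. A reader might also infer that late pain, redness or swelling under other site prefixes is certainly lost. That extends the vasculitis terms by analogy and is not shown.

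**Conclusion.** The point holds as a minor inconsistency with one certain omission. The selection rule in SAP 16.1.3 is narrower than the definition it serves, and any error it causes is a loss of events. The omission of sweating (14 solicited events, 13 rows) needs no assumption about coding, although its effect on the counts depends on whether any late-onset sweating is reported. The loss through unlisted LLTs or other site prefixes depends on coding practice that the documents do not show; it cannot be quantified and may be nil.

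The reach is one supplementary registry summary. A reader might take the gap for a loss of safety data, but the events stay visible in the other tables and the listing. No hypothesis or primary analysis changes, and SAP section 16 plans no statistical comparison between groups on safety.

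**What to change.** In SAP 16.1.3:
- Select late-onset events by PT, as the definition says, and list the PTs treated as synonymous with each solicited event.
- Add a row for sweating, so that the list covers all 14 events of Table E.
- Before unblinding, review the coded unsolicited terms. Include any administration-site or vaccination-site PTs for pain, erythema/redness and swelling that are present. If there are none, record that.
- Repair the broken reference so that it points to Table H, and state whether the LLT codes there serve any purpose other than coding diary events.

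The cost is an edit to a lookup table and its program, plus a short review of coded terms. No new data are needed, and no other output changes.

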10.5.1 Definition of AE

AE Definition

 An AE is any untoward medical occurrence in a clinical study participant, temporally associated with the use of a study intervention, whether or not considered related to the study intervention. 
NOTE: An AE can therefore be any unfavorable and unintended sign (including an abnormal laboratory finding), symptom, or disease (new or exacerbated) temporally associated with the use of a study intervention.

Definition of Unsolicited AEs, MAEs, and Solicited Events		

 An unsolicited AE is an AE that was not otherwise solicited in a participant diary and that is communicated by a participant/participant's caregiver(s) who has signed the informed consent. Unsolicited AEs include serious and non-serious AEs. An unsolicited AE is an AE that was either not included in the list of solicited events or could be included in the list of solicited events but with an onset outside the specified period of follow-up for solicited events. Unsolicited AEs must have been communicated by [participants/ participant's caregiver(s)] who has signed the informed consent. Unsolicited AEs include both serious and non-serious AEs. Potential unsolicited AEs may be medically attended (i.e., symptoms or illnesses requiring a hospitalization, emergency room visit, or visit to/by a healthcare provider). The participant/participant's caregiver(s) will be instructed to contact the study site as soon as possible to report MAEs, as well as any events that, though not medically attended, are of participant/participant's caregiver(s) concern. Detailed information about reported unsolicited AEs will be collected by qualified study site personnel and documented in the participant's records. Unsolicited AEs that are not medically attended nor perceived as a concern by the participant/participant's caregiver(s) will be collected during an interview with the participant/participant's caregiver(s) and by review of available medical records at the next visit. Solicited events are predefined administration site and systemic events for which the participant is specifically questioned, and which are noted by the participant in their diary. Solicited Administration Site Events 
Table 11 Solicited Administration Site Events
 
 
 All Age Subgroups	
 
 Pain	
 
	All Age Subgroups	Pain
All Age Subgroups		
Pain		

Redness														

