Swelling														
• Solicited Systemic Events														
Table 12 Solicited Systemic Events														

  
 All Age Subgroups	
   
 Fatigue	
 
 Fever	
 
 Headache	
 
 Muscle Ache	
 
 Joint pain	
 
 Shivering (Chills)	
 
 Sweating	
 
 Gastrointestinal symptoms:	
 
  Nausea	
 
  Vomiting	
 
  Diarrhea	
 
  Abdominal pain	
  
		All Age Subgroups	Fatigue	Fever	Headache	Muscle Ache	Joint pain	Shivering (Chills)	Sweating	Gastrointestinal symptoms:	Nausea	Vomiting	Diarrhea	Abdominal pain
All Age Subgroups														
Fatigue														
Fever														
Headache														
Muscle Ache														
Joint pain														
Shivering (Chills)														
Sweating														
Gastrointestinal symptoms:														
Nausea														
Vomiting														
Diarrhea														
Abdominal pain														

Events Meeting the AE Definition

 Any abnormal laboratory test results (hematology, clinical chemistry, or urinalysis) or other safety assessments (e.g., ECG, radiological scans, vital signs measurements), including those that worsen from baseline, considered clinically significant in the medical and scientific judgment of the investigator (i.e., not related to progression of underlying disease). Exacerbation of a chronic or intermittent pre-existing condition including either an increase in frequency and/or intensity of the condition. New condition detected or diagnosed after study intervention administration even though it may have been present before the start of the study. Signs, symptoms, or the clinical sequelae of a suspected intervention-intervention interaction. Signs, symptoms, or the clinical sequelae of a suspected overdose of either study intervention or a concomitant medication. Overdose per se will not be reported as an AE/SAE unless it is an intentional overdose taken with possible suicidal/self-harming intent. Such overdoses should be reported regardless of sequelae.

- Significant failure of an expected pharmacologic or biological action.
- Events that occur as a result of protocol-mandated procedures (i.e., invasive procedures, modification of participant's previous therapeutic regimen).

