### 16.1.1. Solicited Adverse Events

Solicited administration site events and solicited systemic events to be summarized are included in [Table E](#). Intensity scales for solicited events (administration site and systemic) are included in [Table F](#) and [Table G](#).

Table E: Solicited events

Solicited administration site events	Solicited systemic events
--------------------------------------	---------------------------

Document: \\ieedc-vnasc01\BIOSdata\GSK\H5N8(Flu)\HAB99808\Biostatistics\Documentation\SAP\SAP\SAP\SAP v5.0\GSK H5N8-219833\_SAP\_v5.0\_19AUG2024.docx

Author: PPD Version Number: 5.0

Version Date: 19AUG2024

Template No.: CS\_TP\_BS016 Revision 7

Reference: CS\_WI\_BS005

Effective Date: 01Nov2021

Pain at Injection Site	Fever
Erythema / Redness at Injection Site	Headache
Swelling at Injection Site	Fatigue
	Muscle ache
	Joint pain
	Shivering (chills)
	Sweating
	Nausea
	Vomiting
	Diarrhea
	Abdominal pain

Table F: Intensity scales for solicited events in adults 18 years of age or older

Adults ( $\geq 18$ years)		
Event	Intensity grade	Parameter
Pain at administration site	0	None
	1	Mild: Any pain neither interfering with nor preventing normal everyday activities.
	2	Moderate: Painful when limb is moved and interferes with everyday activities.
	3	Severe: Significant pain at rest. Prevents normal everyday activities.
Headache	0	Normal
	1	Mild: Headache that is easily tolerated.
	2	Moderate: Headache that interferes with normal activity.
	3	Severe: Headache that prevents normal activity.
Fatigue	0	Normal
	1	Mild: Fatigue that is easily tolerated.

Document: \\ieedc-vnasc01\BIOSdata\GSK\H5N8(Flu)\HAB99808\Biostatistics\Documentation\SAP\SAP\SAP v5.0\GSK H5N8-219833\_SAP\_v5.0\_19AUG2024.docx

Author: PPD

Version Number: 5.0

Version Date: 19AUG2024

Template No.: CS\_TP\_BS016 Revision 7

Reference: CS\_WI\_BS005

Effective Date: 01Nov2021

Adults (≥18 years)		
Event	Intensity grade	Parameter
	2	Moderate: Fatigue that interferes with normal activity.
	3	Severe: Fatigue that prevents normal activity.
Muscle ache all over body	0	Normal
	1	Mild: Muscle aches that are easily tolerated.
	2	Moderate: Muscle aches that interfere with normal activity.
	3	Severe: Muscle aches that prevent normal activity.
Joint pain	0	Normal
	1	Mild: Joint pain that is easily tolerated.
	2	Moderate: Joint pain that interferes with normal activity.
	3	Severe: Joint pain that prevents normal activity.
Shivering (chills)	0	Normal

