	1	Mild: Shivering (chills) that is easily tolerated.
	2	Moderate: Shivering (chills) that interferes with normal activity.
	3	Severe: Shivering (chills) that prevents normal activity.
Sweating	0	Normal
	1	Mild: Sweating that is easily tolerated.
	2	Moderate: Sweating that interferes with normal activity.
	3	Severe: Sweating that prevents normal activity.
Gastrointestinal symptoms: nausea, vomiting, diarrhea and/or abdominal pain	0	Normal
	1	Mild: Gastrointestinal symptoms that are easily tolerated.
	2	Moderate: Gastrointestinal symptoms that interfere with normal activity.
	3	Severe: Gastrointestinal symptoms that prevent normal activity.
Redness at administration site		Record greatest surface diameter in mm

Document: \\ieedc-vnasc01\BIOSdata\GSK\H5N8(Flu)\HAB99808\Biostatistics\Documentation\SAP\SAP\SAP v5.0\GSK H5N8-219833\_SAP\_v5.0\_19AUG2024.docx

Author: PPD

Version Number: 5.0

Version Date: 19AUG2024

Template No.: CS\_TP\_BS016 Revision 7

Reference: CS\_WI\_BS005

Effective Date: 01Nov2021

Adults (<math>\geq 18</math> years)		
Event	Intensity grade	Parameter
Swelling at administration site		Record greatest surface diameter in mm
Temperature		Record temperature in $^{\circ}\text{C}/^{\circ}\text{F}$ . Oral route is preferred.

Table G: Intensity scales for solicited events – erythema / swelling and fever

	Erythema/swelling	Fever (Temp <math>^{\circ}\text{C}</math>)
0:	$\leq 20$ mm	$<38.0$ $^{\circ}\text{C}$ $(<100.4$ $^{\circ}\text{F})$
1:	$> 20 - \leq 50$ mm	$\geq 38.0$ $^{\circ}\text{C}$ ( $100.4$ $^{\circ}\text{F}$ ) - $\leq 38.4$ $^{\circ}\text{C}$ ( $101.2$ $^{\circ}\text{F}$ )
2:	$> 50 - \leq 100$ mm	$\geq 38.5$ $^{\circ}\text{C}$ ( $101.3$ $^{\circ}\text{F}$ ) - $\leq 38.9$ $^{\circ}\text{C}$ ( $102.1$ $^{\circ}\text{F}$ )
3:	$> 100$ mm	$\geq 39.0$ $^{\circ}\text{C}$ ( $102.2$ $^{\circ}\text{F}$ ) - $\leq 40.0$ $^{\circ}\text{C}$ ( $104.0$ $^{\circ}\text{F}$ )
4:		$>40.0$ $^{\circ}\text{C}$ ( $104.0$ $^{\circ}\text{F}$ )

Solicited events will be summarized and listed as:

- The number and percentage of participants, with exact 95% CIs, reporting each individual solicited administration site AE (pain, erythema/swelling, swelling) for all grades, grade  $\geq 2$ , grade  $\geq 3$ , medically attended events during the 7-day follow-up period, and ongoing at the end of the 7-day follow-up period will be tabulated following each vaccination and overall.

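### SAP Table H, the term lookup for the registry summary of late-onset solicited-type events, covers 13 of the 14 solicited events and omits sweating

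*SAP*

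**What the plan says.** SAP section 16.1.3 defines a summary made for registry posting. It counts participants reporting "any unsolicited adverse events with MedDRA PTs that are synonymous with solicited events" with onset after each solicited period, by vaccination, overall and by severity. The section then points to Table H, which "shows the corresponding MedDRA LLTs that will be selected from the unsolicited adverse events for this analysis".

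Sweating is a solicited event throughout the plan:

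- The list of primary safety endpoints in SAP section 16 includes it among the systemic events: "muscle ache, joint pain, shivering [chills], sweating, nausea, vomiting, diarrhea, abdominal pain".
- SAP Table E, the list of solicited events to be summarized (section 16.1.1), includes it.
- SAP Table F gives it its own intensity scale, for example "Moderate: Sweating that interferes with normal activity".
- Protocol section 10.5.1 lists it under "Table 12 Solicited Systemic Events".

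The protocol also settles how a late-onset case is classified. Under section 10.5.1, an unsolicited AE includes one that "could be included in the list of solicited events but with an onset outside the specified period of follow-up for solicited events". The glossary in section 10.7 says the same.

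**The concern.** The definition of the summary makes no exception for any solicited event, whereas the table that carries it out leaves one out. A programmer who selects the Table H terms would produce a posted summary that is silent on late-onset sweating, and a registry reader could not tell whether none occurred or none was looked for. What is at stake is the completeness of one public descriptive table. No hypothesis test, primary endpoint or analysis set depends on it.

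**Working it through.** The plan states no count to reproduce, so the check compares SAP Table E with Table H row by row. Synonyms are matched: erythema with redness, myalgia with muscle ache, arthralgia with joint pain, chills with shivering, and the two spellings of diarrhea.

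| Solicited event (Table E) | Row in Table H |
|---|---|
| Pain at injection site | Pain |
| Erythema / redness | Erythema |
| Swelling | Swelling |
| Fever | Fever |
| Headache | Headache |
| Fatigue | Fatigue |
| Muscle ache | Myalgia |
| Joint pain | Arthralgia |
| Shivering (chills) | Chills |
| **Sweating** | **none** |
| Nausea | Nausea |
| Vomiting | Vomiting |
| Diarrhea | Diarrhoea |
| Abdominal pain | Abdominal pain |

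**Counts**

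- Table E: 3 site + 11 systemic = 14.
- Table H: 3 site + 10 systemic = 13.
- In Table E but not Table H: sweating only.
- In Table H but not Table E: none.
- Share of the list missing: 1/14 = 7.1% of all solicited events, or 1/11 = 9.1% of the systemic ones. These are shares of rows, not of participants or events.

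**Sensitivity to how events are counted.** The intensity scale groups the four gastrointestinal symptoms. If they count as one event, Table E has 14 − 3 = 11 and Table H has 13 − 3 = 10. Sweating is still the only gap.

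**Is the row simply lost from the text?** It does not appear so. All 13 rows carry a term, a code and a decode. Table H runs from chills straight to nausea, and Table E has sweating between those two.

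**Following one case through the plan.** Take non-serious sweating that begins after the 7-day solicited period but within 21 days of a dose.

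1. Protocol 10.5.1 and 10.7 make it an unsolicited AE.
2. It meets the definition of the summary in SAP 16.1.3.
3. No Table H row matches it, so it is not selected.
4. It is still counted in the 21-day unsolicited AE tables of SAP 16.1.2 and shown in the listing of all unsolicited AEs.
5. It should also appear in the table by SOC and PT of "combined solicited and unsolicited non-serious adverse events (all grades, Grade 3, medically attended) during the 21-day follow-up period", planned in the same section.

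**The case against.** The strongest reply is that this is a clerical mismatch with very little consequence. The definition already brings sweating into scope, so the SAP disagrees with itself and no analysis decision is in dispute. The summary is not among the safety analyses in protocol section 9.4.3.2 or the primary safety endpoints in SAP section 16. Sweating within the solicited period is tabulated under 16.1.1, and late-onset sweating appears in other outputs. The row percentages measure no effect on participants.

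Most of this stands, and it is why the point is minor. It does not remove the error. The SAP says the Table H terms are the ones that will be selected, so the natural reading of the table is that it is exhaustive, and following it gives an incomplete posted summary. The output templates (SAP section 8) might show a fuller list, but they are not in the text reviewed, and the SAP's own stated term list is Table H.

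One limit on the reassurance should be noted. The 16.1.2 tables and the combined table cover 21 days after each dose, and only the listing has no such limit. Since the protocol collects unsolicited AEs for 21 days after each dose (section 8.5.1), the practical difference is small.

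**Conclusion.** The point holds, at minor severity and with high confidence. Table H covers 13 of 14 solicited events, sweating is the one missing, and no text justifies leaving it out. The effect is confined to one descriptive registry summary.

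The number of participants affected is unknown, because the documents give no rate of late-onset sweating. It also depends on the layout, which is left to the templates. If the summary only counts participants with any listed event, someone with late-onset sweating and another listed late-onset event would still be counted. If it reports each event separately, sweating would be absent. The conclusion rests on reading Table H as the full selection list, as its introductory sentence indicates.

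**What to change.** Add a sweating row to Table H, with the lower level term and code taken from the MedDRA version in use. The documents do not give the code, so none is proposed here. If the omission was intended, state the reason in 16.1.3.

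Two small items can be settled in the same edit:

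- The paragraph defines the summary by preferred terms, but Table H selects one lower level term per event. Confirm that the listed terms capture what the definition intends. Whether any event is lost this way depends on the MedDRA hierarchy, which the documents do not show.
- Repair the broken cross-reference to the table. This is clerical, since Table H follows directly.

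The cost is one table row, one code lookup and a check of the 13 existing terms. No new data or analysis is needed.
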